#### 9.4.1 Efficacy analyses

**Table 5 - Efficacy analyses**

Endpoint	Statistical Analysis Methods
Primary Change in HbA1c from Baseline to Week 30	
Primary analysis:
 
The primary efficacy endpoint will be analyzed using all HbA1c values at Baseline and Week 30 (observed or imputed), regardless of treatment discontinuation or initiation of rescue therapy (ITT estimand).
 
The primary analysis method for the primary efficacy endpoint will be an ANCOVA model with missing values imputed by MI analysis method in two parts as follows:
 

Missing endpoint data in participants who prematurely discontinue the study treatment before the Week 30 visit will be imputed using a model estimated from participants in the same treatment arm who prematurely discontinue the study treatment before the Week 30 visit but have the measurement for the endpoint (retrieved dropouts). Considering that the number of participants in each treatment arm who discontinue the study treatment but have the measurement for the endpoint is expected to be small, a simple imputation model will be used, where only the baseline measurements are included as the predictor. Each treatment group will have their own imputation model. Missing data will be imputed using the regression method.

Missing endpoint data in all participants, including those in the efpeglenatide arms, who stay on the study treatment until the Week 30 visit will be imputed separately, using a model estimated from participants in the placebo group who stay on the study treatment until the Week 30 visit and have the endpoint data available. The imputation model will include the randomization strata and corresponding baseline values without including any intermediate. Missing data will be imputed using the regression method.

 
In this analysis, missing endpoint values will be imputed 10 000 times to generate 10 000 data sets with complete data. The completed data sets will be analyzed using an ANCOVA model with treatment groups, randomization strata, and geographical regions as fixed effects and the corresponding baseline values as a covariate.
 
The Baseline value is defined as the last available value prior to the first dose administration of IMP or the last available value on or before the date of Randomization if not treated with the double-blinded IMP.
 
The results from the 10 000 analyses will be combined using Rubin's formula and provide the adjusted mean change in HbA1c from Baseline to Week 30 (regardless of treatment discontinuation or initiation of rescue therapy) for each treatment group, as well as the difference between each efpeglenatide dose and placebo and the 95% CI for the difference.
 
A hierarchical procedure will be applied to adjust for the multiplicity of comparison on the primary endpoint:
 

First, the highest dose of efpeglenatide (6 mg) will be compared to placebo to demonstrate superiority of this dose versus placebo

If superiority is demonstrated for efpeglenatide 6 mg, the superiority of 4 mg dose of efpeglenatide versus placebo will be tested

If superiority is also demonstrated for 4 mg dose, the lowest dose (2 mg) will be tested for superiority over placebo

 
When the superiority is not obtained in a step, the sequential testing procedure will be stopped.
 
As noted, the number of retrieved dropouts is expected to be small, and may not have sufficient data to support the imputation approach in item 1 described above. If there are less than 5 participants in any arms who prematurely discontinue the study treatment before the Week 30 visit but have the measurement for the endpoint, a back-up imputation method for the primary efficacy analysis will be used. In particular, missing endpoint data in all participants in both

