2.4.4.1 Analysis of primary efficacy endpoint

The statistical test will be 2-sided tests at a nominal 5% significance level.

Hypothesis Testing of the Primary Endpoint

For the primary efficacy variable of change from Baseline to Week 30 in HbA1c (%), the following statistical null hypothesis and alternative will be tested for each efpeglenatide dose:

- H0: No population LS mean treatment difference in reduction in HbA1c from Baseline;
- H1: Efpeglenatide has a higher population LS mean reduction in HbA1c from Baseline than placebo.

Primary Analysis

The statistical analysis for the primary endpoint is described below.

The Baseline value is defined in [Section 2.1.1](#).

The primary analysis will be an analysis of covariance (ANCOVA) modeling with missing values imputed based upon retrieved dropouts in 2 separates parts as follows:

1. Missing endpoint data in participants who prematurely discontinue the study treatment before the Week-30 visit will be imputed using a model built separately in each arm and estimated from participants in the same treatment arm who prematurely discontinue the study treatment before the Week-30 visit but have the measurement for the endpoint (retrieved dropouts). Considering that the number of participants in each treatment arm who discontinue the study treatment but have the measurement for the endpoint is expected to be small, a simple imputation model will be used, where only the Hb1Ac baseline measurements are included as the predictor. Each treatment group will have their own imputation model. Missing data will be imputed using the regression method.
2. Missing endpoint data in all participants, including those in the efpeglenatide arms, who stay on the study treatment until the Week-30 visit will be imputed separately. The washout-imputation method will be used, where missing endpoint data in the efpeglenatide arms, as well as the missing data in the placebo arm, are imputed from a model estimated from participants in the placebo group with endpoint data without including any intermediate values. The imputation model will include the randomization strata and corresponding Hb1Ac baseline values. Missing data will be imputed using the regression method.

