In this analysis, missing endpoint values will be imputed 10 000 times to generate 10 000 data sets with complete data. The completed data sets will be analyzed using an ANCOVA model with the treatment group (efpeglenatide 2, 4, or 6 mg, or placebo), randomization stratum of Screening HbA1c ($<8.0, \geq 8.0\%$), BMI at Visit 3 ($<30, \geq 30 \text{ kg/m}^2$), and geographical region as fixed classification effects, and Baseline HbA1c value as a continuous covariate.

For subjects with missing efficacy endpoint data at Baseline, values will be imputed using the population mean at Baseline.

SAS pseudo-codes are provided in [Appendix A](#).

The results from the 10 000 analyses will be combined using Rubin's formula, to provide the adjusted mean change in HbA1c from Baseline to Week 30 (regardless of treatment discontinuation or initiation of rescue therapy) for each treatment group, as well as the difference between each efpeglenatide dose and placebo and the 95% confidence interval (CI) for the difference. This will be implemented using MIANALYZE procedure in SAS.

A hierarchical procedure will be applied to adjust for the multiplicity of comparison on the primary endpoint:

- First, the highest dose of efpeglenatide (6 mg) will be compared to placebo to demonstrate superiority of this dose to placebo
- If superiority is demonstrated for efpeglenatide 6 mg, the superiority of 4 mg dose of efpeglenatide to placebo will be tested
- If superiority is also demonstrated for 4 mg dose, the lowest dose (2 mg) will be tested for superiority to placebo

When the superiority is not obtained in a step, the sequential testing procedure will be stopped.

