As noted, the number of retrieved dropouts is expected to be small, and there may not have sufficient data to support the imputation approach in item 1 described above. If there are less than 5 participants in any arms who prematurely discontinue the study treatment before the endpoint visit but have the measurement for the endpoint, a back-up imputation method for the primary efficacy analysis will be used. In particular, missing endpoint data in all participants in both efpeglenatide and placebo groups, regardless of staying on the study treatment or not, will be imputed using a model estimated from participants in the placebo group with endpoint data without including any intermediate values, where randomization strata and corresponding baseline values are included as the predictors. Missing data will be imputed using the regression method.

Sensitivity Analysis

Tipping point analysis

Tipping point analysis based on the same multiple imputation (MI) method as applied above will be performed to examine the robustness of the results from the primary analysis. A penalty δ will be applied to participants in the efpeglenatide group who have no HbA1C data at Week 30. The penalty will be gradually increased to determine at which level (if any) the conclusion of the

analyses in terms of statistical significance is changed for each efpeglenatide dose group. The tipping point is the penalty level at which the magnitude of efficacy reduction in participants without HbA1c data at Week 30 creates a shift in the treatment effect of efpeglenatide from being statistically significantly better than placebo to a non-statistically significant effect. The penalty δ will start at 0 and increase by 0.1 (unit: %) until non-statistical significance is found. Least square mean difference between each efpeglenatide dose and placebo and its associated p-value will be provided for each penalty level.

Analysis on completers

For participants in ITT population who completed the 30-week core treatment period and did not start any rescue therapy before the end of the period, the primary endpoint will be assessed too by the same ANCOVA model as used for the primary analysis using the observed values.

Assessment of missing data

The availability of primary and secondary efficacy data (yes, no) at the endpoint visit (Week 30 or Week 56) will be summarized by treatment status (discontinued, completed) and by treatment group.

Assessment of treatment effect by subgroup

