2.4.4.2.1 HbA1c $<7.0\%$ at Week 30 (yes/no)

Proportions of participants achieving the HbA1c target value of $<7.0\%$ at Week 30 will be compared by treatment group using a Cochran-Mantel-Haenszel (CMH) test stratified by randomization stratum of Screening HbA1c ($<8.0, \geq 8.0\%$) and Visit 3 (Baseline, Day 1) BMI ($<30, \geq 30 \text{ kg/m}^2$) in the ITT population. All HbA1c values at Week 30 will be used to determine whether a participant is a responder (HbA1c $<7.0\%$) or not, even if they are measured after IMP discontinuation or introduction of rescue therapy. Participants with missing HbA1c data at Week 30 will be considered not achieving HbA1c $<7.0\%$. The nominal p-value from the CMH test will be presented. No rounding for HbA1c will be done.

2.4.4.2.2 Changes from baseline in FPG to Week 30 and in body weight to Weeks 30 and 56 and in HbA1c to Week 56

Changes from Baseline in FPG to Week 30, in body weight to Weeks 30 and 56 and in HbA1c to Week 56 will each be analyzed by the same ANCOVA model with missing values imputed by MI method as described in [Section 2.4.4.1](#) the primary analysis. The least squares (LS) means, standard errors of LS means within each treatment group and the adjusted mean and associated two-sided 95% CI of the difference between efpeglenatide 2, 4, and 6 mg and placebo group will be presented.

Summary statistics at protocol scheduled visits and for the last on-treatment value will also be provided for FPG and body weight.

Additional Analysis

Analysis on completers at Week 30 (body weight)

For participants in ITT population who completed the 30-week core treatment period and did not start any rescue therapy before the end of the period, the secondary endpoint of change from Baseline in body weight to Weeks 30, will be assessed too by the same ANCOVA model as used for the primary analysis using the observed values.

Analysis on completers at Week 56 (HbA1c and body weight)

For participants in ITT population who completed the whole on-treatment period and did not start any rescue therapy before the end of the period, the change from Baseline in HbA1c and body weight to Weeks 56, will be assessed by the same ANCOVA model as used for the primary analysis using the observed values.

Sensitivity analysis due to COVID-19 at Week 56 (HbA1c and body weight)

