- PEOT30/56FL is the variable indicating whether the participant prematurely discontinued the study treatment (PEOT30/56FL="Y" if the participants prematurely discontinued the study treatment before Week 30/56 visit and PEOT30/56FL="N" if the participant stay on the study treatment until Week 30/56 visit).
- ARM is the randomized treatment group (Placebo, Efpeglenatide 2mg, Efpeglenatide 4mg, Efpeglenatide 6mg).

- HbA1c_strata is the randomization stratum of screening Hb1Ac (<8%, \geq 8%)
- BMI_strata is the randomization stratum of BMI at Visit 3(<30, \geq 30)
- BASE is the baseline HbA1c.
- AVAL_W30/56 is the change from baseline in HbA1c at Week 30/56.
- W56_missing = “Y” if the Week 56 value is missing, otherwise W56_missing = “N”.
- COVID = “Y” if the missing data is impacted by COVID-19, otherwise COVID = “N”.
- The seed (14822) has been chosen arbitrarily and is based on the study code (EFC14822).

Appendix B Criteria for potentially significant abnormalities - for Phase 2/3 studies (oncology excepted)

Parameter	PCSA	Comments
Clinical Chemistry		
ALT	By distribution analysis: >3 ULN >5 ULN >10 ULN >20 ULN	Enzymes activities must be expressed in ULN, not in IU/L. Concept paper on DILI – FDA draft Guidance Oct 2007. Internal DILI WG Oct 2008. Categories are cumulative. First row is mandatory. Rows following one mentioning zero can be deleted.
AST	By distribution analysis: >3 ULN >5 ULN >10 ULN >20 ULN	Enzymes activities must be expressed in ULN, not in IU/L. Concept paper on DILI – FDA draft Guidance Oct 2007. Internal DILI WG Oct 2008. Categories are cumulative. First row is mandatory. Rows following one mentioning zero can be deleted.
Alkaline Phosphatase	>1.5 ULN	Enzymes activities must be expressed in ULN, not in IU/L. Concept paper on DILI – FDA draft Guidance Oct 2007. Internal DILI WG Oct 2008.
Total Bilirubin	>1.5 ULN >2 ULN	Must be expressed in ULN, not in μ mol/L or mg/L. Categories are cumulative. Concept paper on DILI – FDA draft Guidance Oct 2007. Internal DILI WG Oct 2008.
Conjugated Bilirubin	>35% Total Bilirubin and TBILI >1.5 ULN	Conjugated bilirubin dosed on a case-by-case basis.
ALT and Total Bilirubin	ALT >3 ULN and TBILI >2 ULN	Concept paper on DILI – FDA draft Guidance Oct 2007. Internal DILI WG Oct 2008. To be counted within a same treatment phase, whatever the interval between measurement.

[figure not shown]
Parameter	PCSA	Comments

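### As written, the SAP adjusts the ranked FPG and body weight tests for baseline HbA1c, not for their own baseline: an avoidable loss of precision, mainly for FPG, and in conflict with Protocol Table 5

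*SAP*

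**What the plan says.** **Primary model.** SAP 2.4.4.1 lists treatment, the HbA1c and BMI strata "and geographical region as fixed classification effects, and Baseline HbA1c value as a continuous covariate".

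**Main imputation.** For participants who stop treatment early, "a simple imputation model will be used, where only the Hb1Ac baseline measurements are included as the predictor". For those who stay on treatment, "The imputation model will include the randomization strata and corresponding Hb1Ac baseline values". Appendix A states that "BASE is the baseline HbA1c".

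**Secondary endpoints.** SAP 2.4.4.2.2 takes four endpoints together: Week 30 FPG, Week 56 HbA1c, and weight at both of those visits. These "will each be analyzed by the same ANCOVA model with missing values imputed by MI method as described in" the text on the primary endpoint. No substitution of baseline is stated. SAP 2.4.4.4.2 passes the approach on to FPG at Week 56, and the body weight completer analyses also reuse the primary ANCOVA.

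**Text that points the other way.** Protocol Table 5 describes the ANCOVA with treatment groups, strata "and geographical regions as fixed effects and the corresponding baseline values as a covariate", and its Secondary row applies that model to the continuous secondary endpoints. In the SAP, the back-up imputation is one "where randomization strata and corresponding baseline values are included as the predictors". The Week 56 COVID-19 sensitivity imputation names HbA1c or weight as the baseline predictor, according to endpoint, although its ANCOVA refers back to 2.4.4.1.

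**Text that points the same way.** The protocol synopsis names baseline HbA1c as the covariate of the primary model and sends the continuous secondary endpoints to that model.

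The change logs in SAP 1.5 and 1.6 list no change of covariate.

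**The concern.** In an ANCOVA of change from baseline, the endpoint's own baseline is normally the strongest available predictor, because a high starting value tends to fall and a low one to rise. Baseline HbA1c captures that only to the extent that it correlates with the endpoint's baseline. With HbA1c alone in the model, the residual variance is larger, a chance imbalance in baseline FPG is corrected only in part, and imputed FPG or weight changes depend on HbA1c.

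These are confirmatory tests. In SAP 2.4.4.3 body weight holds ranks 3, 4, 8, 10 and 13, and FPG holds ranks 6 and 7. Testing stops at the first non-significant result, and ranks 8 to 13 are all of the Week 56 tests. A miss on FPG therefore closes all of them. Two programmers could also fit different covariates, obtain different p-values, and both cite the plan.

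**Working it through.** **1. The plan's own power figure.** SAP 1.3 gives 100 per arm, SD 1.1, two-sided alpha 0.05. The SE of a difference is 1.1 x sqrt(2/100) = 0.1556.

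- Difference 0.5: 0.5/0.1556 = 3.214, and Phi(3.214 - 1.960) = 89.5% (noncentral t, 198 df: 89.2%). Stated: 89%.
- Difference 0.6: 0.6/0.1556 = 3.857, and Phi(3.857 - 1.960) = 97.1% (noncentral t: 97.0%). Stated: 96%.

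The figures reproduce to about one point. They concern HbA1c only and are not affected. The documents give no SD, correlation, effect or power for FPG or body weight, so everything below is an assumption shown as a range.

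**2. Precision formula.** Assume equal SD s at baseline and endpoint. Let rho be the correlation between own baseline and endpoint, and r the correlation between own baseline and baseline HbA1c. HbA1c is taken to predict the change only through own baseline. The residual variance of the change is:

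- own baseline in the model: s^2 (1 - rho^2)
- HbA1c only: 2 s^2 (1 - rho) - r^2 s^2 (1 - rho)^2

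The SE ratio is the square root of the second over the first. If the own-baseline test has 90% power, the HbA1c-only test has power Phi(3.2415/ratio - 1.960), where 3.2415 = 1.2816 + 1.9600.

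Worked case for FPG, rho = 0.4 and r = 0.5: own = 0.84; HbA1c only = 1.20 - 0.25 x 0.36 = 1.11; ratio = sqrt(1.11/0.84) = 1.150; power = Phi(2.82 - 1.96) = 80.5%.

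| Endpoint | rho | r | SE ratio | Power, from 90% |
|---|---|---|---|---|
| FPG | 0.4 | 0.5 | 1.150 | 80.5% |
| FPG | 0.4 | 0.7 | 1.104 | 83.6% |
| FPG | 0.5 | 0.5 | 1.118 | 82.6% |
| FPG | 0.5 | 0.7 | 1.082 | 85.0% |
| FPG | 0.6 | 0.5 | 1.090 | 84.5% |
| FPG | 0.6 | 0.7 | 1.062 | 86.3% |
| Weight | 0.93 | 0.1 | 1.018 | 89.0% |
| Weight | 0.97 | 0.1 | 1.008 | 89.6% |
| Weight | 0.99 | 0.1 | 1.002 | 89.9% |

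**3. FPG with unequal SDs.** Assume baseline SD 2.2 to 2.5 and Week 30 SD 2.3 mmol/L, rho 0.3 to 0.5, r 0.5 to 0.8. With rc the correlation between baseline and change, the SE ratio is sqrt[(1 - (rc x r)^2)/(1 - rc^2)].

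- Smallest: baseline SD 2.2, rho 0.5, r 0.8. Variance of change = 4.84 + 5.29 - 5.06 = 5.07; rc = (1.15 - 2.2)/2.252 = -0.466; ratio 1.05.
- Largest: baseline SD 2.5, rho 0.3, r 0.5. Variance of change = 6.25 + 5.29 - 3.45 = 8.09; rc = (0.69 - 2.5)/2.844 = -0.636; ratio 1.23.
- Middle: rc = -0.60, r = 0.65. sqrt(0.848/0.64) = 1.15, or about 80% power.

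**4. Type I error.** Treatment is randomized, so either covariate gives a valid complete-data comparison. Only the variance differs.

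**The case against.** The strongest reply is that this is drafting shorthand. SAP 2.4.4.1 covers the primary endpoint, where naming HbA1c is correct. A strict reading cannot be sustained throughout: it would classify Week 56 endpoints by discontinuation before Week 30 and report adjusted HbA1c means for weight. Appendix A defines its outcome variable as HbA1c change, yet its code comments list the visits to use for body weight, so the HbA1c labels serve partly as placeholders. The SAP log also records that non-primary pseudo code was removed.

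Much of this stands. Own-baseline adjustment may well be what the sponsor intends. A reader might infer stronger claims that the documents do not support:

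- That the SAP newly replaced the protocol's covariate. The protocol synopsis already used the HbA1c wording, so the protocol is itself divided.
- That own baseline appears in the SAP only in the COVID-19 text. The back-up imputation also uses the corresponding baseline and, through 2.4.4.2.2, would reach FPG if triggered.
- That all seven ranked FPG and weight tests are materially weakened. Five of them are weight tests, where the loss is trivial.

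What the reply does not remove is that the SAP passages favouring own baseline concern imputation only. Nowhere does the SAP give the ANCOVA for FPG or weight a covariate other than baseline HbA1c, and 2.4.4.2.2 leaves the reader to guess the substitution.

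**Conclusion.** The point holds as an inconsistency with Protocol Table 5 and an avoidable loss of precision. It is a free improvement, not a threat to validity. A reader might infer biased estimates or an inflated false-positive rate. The choice of covariate causes neither in the complete-data comparison, and what it would do through the imputed values cannot be sized, because the documents give no expected amount of missing data.

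Only FPG is likely to notice. Its standard error would be about 5 to 23% larger, centrally 6 to 15%, and over the central range 90% power becomes about 80 to 86%. Those figures rest on assumed SDs and correlations, on an assumed 90% reference power, and on HbA1c acting only through baseline FPG. Region and the strata are left out of the calculation. They are not properties of this trial. For body weight the loss is under about 2% of the standard error, and the BMI stratum already carries part of baseline weight. The HbA1c models are unaffected, although the Week 56 HbA1c tests can be reached only if both FPG tests succeed.

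**What to change.** In SAP 2.4.4.2.2, state that for each continuous endpoint the baseline value of that endpoint (FPG for FPG, body weight for body weight) replaces baseline HbA1c as the ANCOVA covariate and as the baseline predictor in the imputation models, as in Protocol Table 5. In Appendix A, define BASE and the outcome variables as belonging to the endpoint being analyzed. Change covariate and predictor together: imputing from HbA1c while adjusting for own baseline would leave the imputed values largely unrelated to the covariate.

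The cost is one sentence and a variable definition. Both baselines are already collected under the Schedule of Activities, so no new data are needed. It should be written before unblinding, so that the choice of covariate cannot look data-driven.
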